Outcomes: Primary outcome: **The percentage of women with triage smears at 120 days after HPV results are registered in SITAM.** This will allow measurement of the overall effect of the multi-component intervention including two periods: a) the 60 day period between the Test results and the SMS message and e-mail sent to CHWs (days 1-59); and b) the 60 day period between the SMS message and e-mail sent to CHWs and triage measurement (days 60-120). **Secondary outcome:**

[figure not shown]

Figure 1. The multi-component mHealth Intervention

[figure not shown]

Figure 2. Health Belief Model, adapted from Janz and Becker 1984⁵⁷

The percentage of women with triage smears at 60 days after Test Results, when the first SMS message is sent (days 1-59). This outcome will allow us to measure the individual effect of the SMS messages sent to women (before CHWs receive prompts to contact non-compliant HPV+ women).

[figure not shown]
Participant inclusion criteria: Women aged 30+ that have performed HPV self-collection offered by CHWs during routine home visits. Participants must be competent to understand the consent form, able to communicate with study staff, and provide a working mobile phone number capable of receiving calls and SMS messages.

Study procedures. CHWs from both groups will identify eligible women and invite them to participate in the study during their routine home visits. Once women have performed HPV-self collection, CHWs will screen for eligibility criteria, including use of mobile phones. CHWs will ask women whether they would provide a working mobile phone number capable of receiving calls and SMS messages. Those women who would provide such telephone number will be explained the study objectives and will be invited to participate in the study. Women accepting to participate will be asked to provide the telephone number. Based on a mHealth study in Northern Argentina among women with Chagas disease,³⁵ and a mHealth study in Buenos Aires among poor population with high blood pressure,⁶⁰ we expect approximately 85% of women will provide a telephone number; with 70% providing their own personal mobile phone.

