MH Group: CHWs will carefully explain participants the sequence of SMS messages to be received depending on the Test results, and how they should proceed after reception of the SMS messages. If the woman does not have a personal phone, she will be asked if she is willing to be contacted and receive the proposed SMS messages on a shared phone. CHWs will inform women about the nature and content of the SMS messages to be received. They will also explain that they might come back for a personal visit if they have not performed triage 60 days after the test results. Therefore, consent to participate also means women agreement to be contacted and receiving SMS messages, even if phones are shared by several family members.

Women with positive self-collected tests will receive a multi-component intervention (Figure 1). Upon registration in SITAM of the HPV result at the laboratory, they will receive a weekly SMS message for four weeks, notifying them that the test results are available, and they should go to the health center. Messages will be stopped if a Pap result is registered in SITAM.

Sixty days after the date of the Test result, CHWs will receive an e-mail and SMS message informing them that there are HPV+ women who have not had Pap triage (if this is the case). The e-mail will also contain a secure link to the list of HPV+ women to be visited, as explained above. CHWs will be asked to confirm receipt of the e-mail for monitoring project processes. CHWs will visit these HPV+ women within 15 days of being notified, for an in-person reminder and counseling about the importance of attending health centers and have triage performed. The script for this visit will be developed based on the results of the FGD using HBM concepts to address issues of perceived susceptibility, perceived severity, and benefits of triage. If possible, CHWs will also provide support to address barriers (e.g., connecting women with transport available in some municipalities). We will track CHW visit information on the Trial form, including visit attempts, date of visit and issues addressed during counseling. The subgroup of HPV+ women visited by CHWs are given 30 days to

get screened as we consider that they are probably women facing specific obstacles (i.e. lack of transportation) and might need additional time to solve them. This timeline is in agreement with programmatic organization of the cervical cancer prevention process.

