Randomization and sample size calculations: All CHWs (clusters) (approximately 700) of the Jujuy province offer self-collection and will be eligible to participate in the study. After classifying them into four groups according to gender and urban/rural setting, a stratified sample of 240 CHWs will be randomly selected with allocation proportional to strata. Selected CHWs will be invited to participate in the study following the order defined by the random list until 200 are enrolled. Enrolled CHWs will be randomly allocated to the MH or the UC group (3:2 ratio). The statistician will produce computer-generated random number lists for the CHW selection and the intervention allocation. Allocation concealment is guaranteed because all CHW will be assigned to the trial arms at the same time. Blinding of intervention and outcome assessments is not feasible due to the characteristics of the study. The number of CHWs was defined based on pragmatic considerations. From our experience¹⁴, this is a feasible number of CHWs that can be enrolled in the trial and trained in programmatic, routine conditions. We decided to allocate a larger number of CHWs to the MH group to be able to detect changes in the time series trend associated with the second component of the intervention

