(see Analysis Plan below). In addition, a larger number of CHWs in the intervention group will benefit the assessment of the implementation outcomes. Based on PHC records and previous experience¹⁴ we estimate that each CHW will enroll an average of 20 eligible women in a 10-month period. We assumed an attrition rate of 20% due to problems with mobile phones (i.e. non-identified number, unpaid phone bill, lack of signal, etc.), SMS messages not delivered and/or other issues. Under a 13% prevalence of HPV+ in this population,¹¹ we estimate that each CWH will contribute with an average of 2 HPV+ women. **Primary outcome:** The target sample size (120 CHWs in the MH group and 80 CHWs in the UC group, each one providing 2 HPV+ women) will have 97% power to detect a 20% triage difference between the two groups when the control group has a 30% triage in a 120-days period (two-sided test, alpha=0.05). Correlation induced by the CHWs was included in power calculations assuming an intra-class correlation coefficient of 0.10. **Secondary outcome:** Under the same assumptions, the proposed sample size will have 90% power to detect a difference of 10% in triage between groups when the control group has a 15% triage by day 60.

A specifically built database will be used (RCT database), combining information from the Trial Form, the AS Monitoring Registry, and SITAM, the national screening information system.⁵² The Trial Form will register information about the randomization group, agreement to participate in the study, women's socio-demographic data, and tasks performed by the CHWs (contact after reminder and reasons of no contact). Data on HPV testing, triage, diagnosis and treatment will be uploaded importing data from SITAM, linking the records through each woman's national identification number. The AS Monitoring Registry will include data from the Automated System regarding receipt of confirmatory SMS messages and e-mails, and valid phone numbers and e-mails. Data entry will be done through specific software that will include range and inter-item consistency checks. Data will be stored in files compatible for analysis with statistical packages (Stata).

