Analysis plan: All analysis will be conducted on an intention-to-treat (ITT) basis; the effect of the multi-component mHealth intervention on the primary outcome will be assessed using a generalized estimating equations approach. The model (logit link, and binomial distribution) will include trial group as fixed effect and CHWs as the clustering variable. Potential effect modification due to rural/urban location of the woman and CHW gender will be evaluated. Baseline socio-demographic characteristics of the women will be compared between groups using the same model with link and distribution selected depending on the variable. Factors showing clear unbalance between arms will be included in the model proposed above to adjust for potential confounding. The same approach will be used to estimate the intervention effect on the secondary outcome. Analyses will be conducted using STATA 14.0 or SAS v.9.4. The trial will follow the CONSORT extension for cluster randomized trials reporting guidelines.⁶³

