Potential problems and limitations: One of the potential limitations of randomization of CHWs is the **risk for contamination** due to CHWs assigned to different study groups, but working in neighboring areas, which could activate CHWs and women in the UC group. However, our prior work using CHW cluster randomization¹⁴ suggests that this risk is low and the effect of contamination is minimal. If such effect occurs, we expect them to be moderate because meaningful improvements in adherence to triage require a systematic effort to address problems related to follow-up adherence which are unlikely to occur in the absence of a specific intervention. Also, **it is not possible to blind CHWs (clusters) or women in this study.** However, laboratory personnel processing the HPV-test and personnel entering data in SITAM, the national screening information system, will be blind. Moreover, the assessment of primary and secondary outcomes will be objective, as data on triage is extracted from SITAM. Nevertheless we will compare demographics characteristics and screening history of women enrolled in the two study groups and will control in the analysis for any variable showing unbalance between study groups. Other problems that might affect the RCT are those related to **poor cell phone network coverage or reception or gaps in service due to unpaid telephone bills.** However, the sample size calculations accounted for this type of attrition, as described above. Finally, **if women do not confirm their identity within one week of initial SMS**

message reception, it will affect the delivery of the intervention (number of SMS messages the woman will receive). To minimize this potential problem, CHWs will emphasize the importance and ease of confirming identity as soon as possible, ideally within 24 hours, not exceeding 7 days.

We **evaluated and ruled out alternative designs** such as having a three group trial (comparing SMS messages to women vs. SMS messages to women + SMS message and e-mail to CHWs vs. UC) because the main aim of the trial is to assess the effect of the multi-component intervention, not each component separately. In addition, such a trial should include a larger number of CHWs, which would attempt against feasibility of a study that will take place in a real-world, programmatic context. Instead, we propose a time series approach to explore the differential impact of each component of the intervention.

Safety and monitoring

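### The day-60 outcome is described as the effect of the SMS alone but compares the whole package before CHW prompts, and the time series meant to assess the CHW prompt is absent from the Analysis plan

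*Combined protocol and SAP*

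**What the plan says.** All references are to the combined protocol and SAP.

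- **Outcomes.** The primary outcome is triage by day 120. The section splits follow-up into days 1-59 and days 60-120, with the break at the CHW prompt. The secondary outcome, triage by day 60, is said to "measure the individual effect of the SMS messages sent to women (before CHWs receive prompts to contact non-compliant HPV+ women").
- **Study procedures, MH Group.** At enrolment the CHW explains the message sequence and what to do on receiving it. On the later visit: "They will also explain that they might come back for a personal visit if they have not performed triage 60 days after" the test results. The UC text has routine counselling and advice to collect results within a month; it announces no visit.
- **Randomization and sample size calculations.** The larger MH arm is chosen "to be able to detect changes in the time series trend associated with the second component of the intervention". The next words are "see Analysis Plan below). In addition, a larger number of CHWs in the intervention group will benefit the assessment of the implementation outcomes", which give both the pointer to the method and a second reason for 3:2.
- **Potential problems and limitations.** A three-group trial was rejected because the main aim concerns the whole intervention. "Instead, we propose a time series approach to explore the differential impact of each component of the intervention".
- **Analysis plan.** A GEE logistic model for day 120, with trial group as fixed effect and CHW as cluster. For day 60: "The same approach will be used to estimate the intervention effect on the secondary outcome".
- **Planning rates.** The primary power is "to detect a 20% triage difference between the two groups when the control group has a 30% triage in a 120-days period"; the secondary power is "to detect a difference of 10% in triage between groups when the control group has a 15% triage by day 60".

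**The concern.** Two statements about components go further than the design and the plan allow.

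First, a contrast between arms estimates everything that differs between them up to that time. If MH women receive more than SMS before day 60, the day-60 difference cannot be called the individual effect of SMS.

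Second, an analysis that helps justify the allocation ratio and stands in for a third arm should be defined before data are seen. Here the series, the unit of time, the model and the comparator are open. The comparator matters most: UC women also attend triage after day 60, so a change seen only within MH mixes the prompt with uptake that would have happened anyway.

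What is at stake is what the trial may say about SMS and CHW prompts separately, which bears on scale-up. The day-120 comparison is not at stake.

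**Working it through.** **Step 1. What differs between the arms before day 60.**

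| Before day 60 | MH | UC |
|---|---|---|
| Weekly SMS for four weeks after a positive result | yes | no |
| Explanation of the messages and how to proceed | yes | no |
| Told that the CHW may visit if untriaged at day 60 | yes | no |
| CHW prompt and visit | not yet | no |

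The parenthesis in the Outcomes section correctly excludes the last row. The second and third rows remain with the SMS. The explanation can be seen as part of delivering SMS; the announced visit cannot, since it belongs to the second component. MH CHWs also get extra training in counselling women who miss triage, but nothing shows it being used before day 60, so I do not count it. No passage gives a size for the non-SMS rows.

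**Step 2. Is the time series specified anywhere?** The Outcomes section supplies the two periods. The Analysis plan has the GEE, effect modification by location and CHW gender, adjustment for imbalance, and the same model for day 60. It has no time term, series or comparator. The Quantitative data analysis section under Aim 2 covers only the two surveys. No power for the time series can be computed, because there is no model.

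**Step 3. Reproduce the plan's power.** Inputs: 160 UC and 240 MH women, ICC 0.10, two per CHW, two-sided 0.05. Design effect = 1 + (2 - 1) x 0.10 = 1.10, so effective sizes are 145.5 and 218.2. With power = Phi{[(p2 - p1) - 1.96 x SE0] / SE1} (SE0 pooled, SE1 unpooled):

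- Day 120, 30% vs 50%: SE0 = 0.0528, SE1 = 0.0509; (0.20 - 1.96 x 0.0528)/0.0509 = 1.90; power 97.1%. The plan states 97%.
- Day 60, 15% vs 25%: the same formula gives 63.7% where the plan states 90%. That is a separate matter, and the 90% is not used here.

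**Step 4. Does UC uptake continue after day 60?** Assumption: the two power scenarios form one path (UC 15% then 30%; MH 25% then 50%). The plan does not say so.

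| | UC | MH |
|---|---|---|
| Gain by day 60 | 15 points | 25 points |
| Gain after day 60 | 30 - 15 = 15 points | 50 - 25 = 25 points |
| Risk by day 60 | 15.0% | 25.0% |
| Risk after day 60 among untriaged | 15/85 = 17.6% | 25/75 = 33.3% |
| Change in risk | +2.6 points | +8.3 points |

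On the cumulative scale neither arm shows a change in trend. On the conditional-risk scale UC matches 2.6 of MH's 8.3 points, about 32%. What a within-MH reading would credit to the prompt therefore depends on the scale, which the plan does not choose.

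**Step 5. Is a between-arm replacement workable?** On the same path, 160 x 0.85 = 136 UC and 240 x 0.75 = 180 MH women are untriaged at day 60. Using the Step 3 formula with 136/1.10 and 180/1.10, 17.6% vs 33.3% has 85.7% power. Expected odds ratios, with SE of the log odds ratio = sqrt{1.10 x [1/(n1 p1 q1) + 1/(n2 p2 q2)]}, where q = 1 - p:

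- Days 1-59: (25/75)/(15/85) = 1.89, SE 0.280, 95% CI 1.09 to 3.27.
- Days 60-120: (33.3/66.7)/(17.6/82.4) = 2.33, SE 0.288, 95% CI 1.33 to 4.11.

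The intervals overlap widely. Each period can be described, but the pair does not rank the components. These figures describe the proposed replacement, not the protocol's undefined series.

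**The case against.** The protocol is open about its ambition: the component analysis is offered to explore, separating components is not the main aim, and 3:2 has a second reason in the implementation outcomes. The Outcomes section defines both periods and limits the day-60 claim to before CHW prompts. The Analysis plan itself calls the day-60 estimate an intervention effect, so a report attributing it to SMS alone is possible rather than certain. Explaining the messages is arguably inseparable from sending them. All of this stands, and it makes the point minor. It does not remove the announced visit from the day-60 contrast or put a method where the cross-reference sends the reader.

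Three stronger readings are tempting but unsupported:

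- **That 15 of MH's 25 later points would be wrongly credited to the prompt.** That is a share of the gain after day 60, not of a change in trend, and no passage excludes UC from the series.
- **That the trial has been shown to lack power to separate components.** There is no time-series model whose power could be computed.
- **That the 3:2 ratio is unjustified.** The second reason stands by itself.

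**Conclusion.** The point holds, as a minor one. The day-60 comparison is valid and randomised, but its estimand is the MH package before CHW prompts. The size of the non-SMS part is unknown: a reader might infer that the SMS effect is materially overstated, and the documents show neither that nor the opposite. The time series is relied on twice and specified nowhere beyond its two periods. A change read within MH alone could not separate the prompt from uptake that also continues under UC, from 15% to 30%, if the two power scenarios are one path. The textual findings need no numerical assumption. The primary analysis, design and sample size are unaffected.

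**What to change.** 1. **Outcomes.** Describe the day-60 outcome as the effect of the MH package before CHW prompts: the SMS, the explanation that goes with them, and the announced possible visit.
2. **Time series.** Choose one:
   - Delete the references in Randomization and sample size calculations and in Potential problems and limitations, and rest 3:2 on the implementation outcomes.
   - Or state in the Analysis plan an exploratory between-arm analysis with UC as concurrent comparator: the arm effect with 95% CI, by GEE logit clustered on CHW, for days 1-59 and for days 60-120 among women untriaged at day 60. Date triage by one stated rule in both arms, either smear date or SITAM registration. The rule matters because the outcome counts smears, elsewhere the text refers to registered results, and reports take a mean of 15 days.
3. **Limits, if the second option is chosen.** State that the second period conditions on post-randomisation status, includes carry-over from the earlier components, and supports no claim of differential component impact. No test comparing the two periods is needed.

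Cost: wording, and at most one exploratory analysis on data already planned for the RCT database. The downside is a more modest claim about components.

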All SMS messages and e-mails will comply with security procedures according to NIH Human Protection Subject Guidelines [47]. The PI will be responsible for monitoring of adverse events and data quality and safety, as this is a low-risk investigation. The Plan for monitoring of data quality and accuracy will include the following: Data entry from the CRT will be done through specific software that will include range and inter-item consistency checks. Entries out of the expected range will not be permitted. Re-entry of 20% of questionnaires will be done for quality control. The data cleaning process will actively search for errors in a planned way.

SPECIFIC AIM 2: To evaluate the implementation strategy and identify barriers and facilitators to implementation of the multi-component mHealth intervention.

RE-AIM and CFIR frameworks will guide the implementation evaluation: as illustrated in Figure 5. The CFIR comprises 39 common constructs from published implementation frameworks and models and organizes them into five major domains.⁴⁵ In this study we will analyze the following domains:

Intervention Characteristic (Relative advantage; adaptability; complexity and cost); **Outer Setting** (Patient needs and resources; external policies and incentives); **Inner Setting** (Structural characteristics; tension for change, relative priority and available resources; access to knowledge and information); and **Characteristics of Individuals** (Knowledge and beliefs about the intervention; perceived self-efficacy).⁴⁵ Proposed quantitative and qualitative measures based on RE-AIM and CFIR frameworks are presented in Table 1.

[figure not shown]

Figure 5. Implementation evaluation. Adapted from Damshroder et al., 2015.⁶⁴

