Finally, we will carry out a **Structured questionnaire among HPV+ women (Women Survey)** to evaluate their acceptability of the strategy, their perspectives about the implementation, and reasons for adherence and non-adherence to triage. We will survey all HPV+ women from the RCT intervention group (approximately 240 women), 5 months after the HPV test result (this is, one month after measurement of the primary outcome), irrespective of their triage status. The questionnaire will include open and closed questions with dimensions related with women's experiences and

Table 1. Measurements and data sources proposed for Implementation Evaluation based on RE-AIM and CFIR

	Quantitative outcomes	Qualitative evaluation	Data source
Reach Representativeness of women reached by the intervention (quantitative data)	-% of eligible women who accepted to participate in the study -Socio-demographic information of participant/non-participant women		RTC database (Trial Form)
Effectiveness in increasing women's adherence to triage (quantitative and qualitative data)	-Primary outcome: percentage of women with triage smears 120 days after test results are registered in SITAM.	Reasons for adherence/non adherence to triage.	RCT database (SITAM) HPV+ Women Survey
Adoption by CHWs of the strategy of visiting HPV+ women after receiving SMS messages and e-mails*	-% of CHWs that visited at least one HPV+ women after receiving the SMS message and e-mail.		RCT database (Trial Form+Automated System Monitoring Registry)
Acceptability of the intervention by adopters	-% of CHWs that agreed with programmatic incorporation of the mHealth intervention.	CFIR construct: Knowledge and beliefs about the intervention; perceived self-efficacy	Self-administered semi-structured survey of CHWs
Implementation of intervention activities according to protocol (quantitative data)	-% of randomized CHWs that participated in trainings. -% of SMS messages that reached a valid phone number. -% of HPV+ women who sent confirmatory SMS messages. -% of e-mails that reached a valid e-mail address. -% of CHWs who sent confirmatory e-mails.		Automated System Monitoring Registry and Training Attendance List

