Acceptability of the intervention by women. (quantitative and qualitative data)	-% of women who accept and are satisfied with the intervention.	Women level Experience and perception of the intervention; acceptability of SMS messages, pertinence of frequency, reception time and content of SMS messages.	HPV+ Women Survey
Barriers and facilitators to implementing and administering the intervention (qualitative data)		Stakeholder/CHWs level CFIR constructs: Relative Advantage; Adaptability; complexity and cost. Patient Needs & Resources and External Policies & Incentives. Structural Characteristics; Tension for Change; Relative Priority and available Resources, Access to Knowledge & Information.	Semi-structured interviews with stakeholders and Self-administered semi-structured survey of CHWs
Maintenance		Intention to incorporate the strategy.	Interview with Stakeholders

*Adoption of the Automated System will not be measured as it will be a unique centralized system linked to SITAM

perceptions, including acceptability and relevance of SMS message frequency, receipt time, and content; perceived effect of the multiple components of the intervention on their adherence, and reasons for adhering/not adhering to triage. The nominated list of these women and their contact details will be extracted from the RCT database. Trained interviewers will contact these women via telephone to make an appointment to visit them at their homes to administer the questionnaire. The training will be carried out by the project staff; it will include formal aspects regarding applying the questionnaire as well as skills for developing a connection with the interviewees. Interviewers will be provided with a list of women to interview with contact information.

Quantitative data analysis. This section refers to the analysis of data from the Women Survey and the Self-administered semi-structured survey of CHWs. A descriptive analysis of each study dimension will be carried out using simple frequencies and percentages for each of the variables under study. The association between the variables will be measured using the Chi square test of independence. Outcomes will be summarized as percentages and compared across women/CHWs socio-demographic characteristics using logistic regression. Results will be presented as estimates and 95% confidence intervals. Analysis will be conducted using STATA (version 13.0) and/or SAS (version 9.3).

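### Adverse-event monitoring is assigned to the PI, but no data source is described as asking about harm from the messages, so a count of zero could not be interpreted

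*Combined protocol and SAP*

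**What the plan says.** The Safety and monitoring section gives the task to one role: "The PI will be responsible for monitoring of adverse events and data quality and safety, as this is a low-risk investigation". The only plan set out after it opens with "The Plan for monitoring of data quality and accuracy will include the following" and lists range and consistency checks, re-entry of 20% of questionnaires, and data cleaning. It does not define an adverse event or give a form, question, timing or reporting route for one.

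The trial database is built by "combining information from the Trial Form, the AS Monitoring Registry, and SITAM, the national screening information system" (Randomization and sample size calculations). The automated system's registry holds data "regarding receipt of confirmatory SMS messages and e-mails, and valid phone numbers and e-mails".

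Under Study procedures, MH Group, a woman without her own phone is asked whether she accepts messages on a shared one, and "consent to participate also means women agreement to be contacted and receiving SMS messages, even if phones are shared by several family members". The Trial Form's visit section, for MH women without triage at day 60, covers availability, reasons for not attending, support needs and action taken.

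The Women Survey (Specific Aim 2) goes once, five months after the result, to all HPV+ women in the MH arm. It has open and closed questions on experiences and perceptions, "including acceptability and relevance of SMS message frequency, receipt time, and content", plus perceived effect and reasons for adhering or not. Table 1 lists process measures such as the percentage "of SMS messages that reached a valid phone number" and, separately, the percentage of HPV+ women who sent a confirmatory message.

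**The concern.** The risks of this intervention are social and psychological. Someone else may read a message, a result may become known against the woman's wish, or the contact may cause distress or a problem at home. The decision to allow shared phones makes disclosure foreseeable. The messages are described as saying that results are available, not what they are. However, the weekly series is described only for HPV+ women, so its pattern might be informative. What HPV-negative women receive is not clear from the text.

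If nobody asks about these events, they cannot be recovered at analysis. The Overview and Design section uses minimal risk as one reason for the hybrid design, and the Impact and Future Directions section looks ahead to scale-up. A report of no adverse events would be read in that context, and the data behind it could not support it.

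**Working it through.** **1. Each source against the harms of interest**, using only the content that the plan describes.

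| Source | Described content | Could it catch harm? | Limits |
|---|---|---|---|
| Trial Form, day-60 section | Reasons for not attending, support needs, action taken | If volunteered | MH arm; only women without triage at day 60 |
| Automated system registry | Valid numbers, confirmations | A missing confirmation is an indirect sign of a wrong recipient | Cannot show disclosure on a correctly registered shared phone |
| SITAM | Tests, triage, diagnosis, treatment | No described route | – |
| Women Survey | Experience, acceptability, reasons | If volunteered to an open question | MH arm; once, at month 5 |
| CHW survey | Open-ended questions, barriers | If volunteered by a CHW | Anonymous; 8 weeks after the trial |

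No row contains a described question about harm, and no row is linked to the PI's task.

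**2. Number of women.** The plan has 120 MH CHWs with 2 HPV+ women each: 120 × 2 = 240, which reproduces the plan's approximate survey size. Unrounded: 120 × 20 × 0.80 × 0.13 = 249.6.

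**3. Exposure through another person's phone.** Study procedures expects 85% to give a number and 70% to give their own phone.
- If 70% is a share of all women: (85 − 70)/85 = 17.6%; 0.176 × 240 ≈ 42.
- If 70% is a share of those giving a number: 30%; 0.30 × 240 = 72.

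**4. Reach of the day-60 visit.** The secondary-outcome planning figures (15% plus a 10-point difference) imply 25% triaged in the MH arm by day 60. The visit list would then hold 0.75 × 240 = 180 women, and 60 would not be asked there.

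**5. What a zero means without solicitation.** Let r be the true rate of harm and c the fraction of harms that reach a record. Then P(at least one report) = 1 − (1 − r·c)^240. The documents give neither r nor c; the values below are assumptions.

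| r | c = 10% | c = 50% | c = 100% |
|---|---|---|---|
| 1% | 0.21 | 0.70 | 0.91 |
| 2% | 0.38 | 0.91 | 0.99 |

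At r = 2% (0.02 × 240 = 4.8 women expected to be harmed) and c = 10%, a zero count has probability 1 − 0.38 = 0.62. Zero reports bound only the product r·c: 1 − 0.05^(1/240) = 1.24% (one-sided 95%). The bound on r is about 1.24%/c, which is 2.5% at c = 50% and 12.4% at c = 10%. Because c is unknown, there is no usable bound on r.

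**6. What a zero means with solicitation** (c taken as 1, women treated as independent).
- All 240 answer: 1 − 0.05^(1/240) = 1.24%.
- Assumed 60% response, 0.60 × 240 = 144: 1 − 0.05^(1/144) = 2.06%.
- The upper limits of the two-sided 95% interval, using 0.025 in place of 0.05, are 1.53% and 2.53%.

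**The case against.** A reader might infer that none of the sources can record harm, so that monitoring must return zero whatever happens. The documents do not support that. The Women Survey is a home interview with open questions on experience, the CHW survey has open-ended questions, and the visit section takes reasons and support needs. Under the assumed values above, the chance of at least one report ranges from 0.21 to 0.99. The survey topics are also introduced as examples, not as a closed list.

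A reader might also take the Table 1 measure of messages reaching a valid number as counting a stranger's receipt as delivery to the woman. It makes no such claim, and the same table reports confirmations separately. Under Potential problems and limitations the plan says "CHWs will emphasize the importance and ease of confirming identity as soon as possible, ideally within 24 hours, not exceeding 7 days", and a missing confirmation is recorded.

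Other safeguards count too. Shared-phone use requires the woman's agreement after she is told the nature and content of the messages. Their wording is developed in focus groups and validated. The described text does not state a positive result. The risk is plausibly low, and 42 to 72 women on another person's phone are not 42 to 72 harms.

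Finally, the questionnaires and Trial Form are not reproduced and consent pages were removed from the available text. A harm item or contact route may exist there.

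All of this stands. It does not supply a described question about harm, or a route from any source to the PI. Confirmation of identity does not detect disclosure on a shared phone that was correctly registered.

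**Conclusion.** The point holds as a gap in ascertainment. Monitoring of adverse events is assigned, but no source is described as soliciting or recording harm from the intervention. The channels that might catch it depend on volunteered or indirect information, come mostly late, are not tied to the PI, and allow no comparison with usual care. Under-ascertainment is likely, and a zero count could not be interpreted.

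The size is an exposed group of about 42 to 72 of 240, depending on how the 70% is read and assuming that the ownership figures apply to HPV+ women. Solicitation would turn a zero into a bound of about 1.2% with full response or 2.1% at an assumed 60% response. Both bounds assume independent women, complete recall and honest answers, and that non-responders resemble responders. The primary and secondary effectiveness analyses are not affected. This is an inexpensive improvement that should be made; it is not a threat to the trial's main conclusion.

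**What to change.** 1. Add three closed items to the Women Survey: whether anyone else read or received the messages; whether anyone learned the result through them against her wish; whether this caused distress or a problem at home.
2. Add one matching line to the day-60 visit section of the Trial Form.
3. In Safety and monitoring, name these items and missing identity confirmations as what the PI reviews as forms arrive. Visits and interviews occur woman by woman, so early reports could reach the PI during the 10-month enrolment.
4. Add a Table 1 row giving the survey items with a 95% CI, the number who answered and the response rate.
5. State the limits: MH arm only, with no usual-care comparison; survey at month 5; visit only for women without triage at day 60.

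If the existing forms already carry such items, steps 1 and 2 reduce to naming them in Safety and monitoring.

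The cost is three survey questions, one line on an existing form, one table row and a slightly longer interview, and the safety statement may become less favourable. Randomization, outcomes and sample size do not change. The survey falls after the 120-day outcome, so its items cannot influence that outcome.
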